5.3.4 Safety Variables

Safety will be assessed descriptively based on:

- Adverse events (AE)
- Serious adverse events (SAE)
- Clinical laboratory values (hematology, clinical chemistry and urinalysis)
- Vital signs
- Local tolerability

Major Cardiac, Cerebrovascular and Thrombotic Events Adjudication Committee

An independent adjudication committee will be used to adjudicate all observed cardio- and cerebro-vascular events reported during the conduct of the study to assure consistent assessment of major cardiac, cerebrovascular and thrombotic events. The events that are adjudicated and the adjudication process will be detailed in the CCVT Adjudication Committee Charter. Site personnel will collect source documentation for the identified events and submit to the CCVT Adjudication Committee. Source documentation should be obscured before submission by site personnel.

Source documentation: (below types of source may be included with the case and will vary depending on type of event and available source):

- SAE form or narrative
- Hospital Discharge Summary

- Death Summary/Details of death note
- Local Lab Values (e.g., normal ranges; cardiac biomarkers)
- Imaging reports (e.g., X-Ray, CT, MRI, MRA, Angiography, Ultrasonography)
- Consultation Notes (e.g., Cardiology, Neurology)
- Procedure Reports (e.g., cardiac catheterization, PCI, CABG)
- Echocardiography
- Admission History/Emergency Room report
- Autopsy result
- Death Certificate
- Clinical Course (e.g., progress notes, doctor visit notes)
- Narrative Form
- ECG
- Other Source (specified)

Details to perform the assessments and complete the necessary documentation will be available in the adjudication charter and investigator training material.

5.3.5 Pharmacokinetic Variables

Risankizumab plasma concentrations will be determined. Descriptive statistics will be calculated for each sampling time. PK and ADA data may be combined with data from other studies and analyzed using a mixed-effects modeling approach. This analysis will estimate the population central value and the empirical Bayesian estimates of the individual values for risankizumab apparent clearance (CL/F) and volume of distribution (Vss/F). Additional parameters may be estimated if useful in the interpretation of the data. Relationships between exposure and clinical observations (efficacy or safety variables of interest) may be explored.

The number and percentage of subjects with ADA will be calculated. As appropriate, the effect of ADA on risankizumab pharmacokinetics and efficacy may be explored.

5.4 Removal of Subjects from Therapy or Assessment**5.4.1 Discontinuation of Individual Subjects**

All subjects have the right to withdraw from the study at any time without the need to justify their decision. The investigator has the right to remove subjects from the study for noncompliance, administrative or other reasons. It should be clearly understood that an excessive rate of withdrawals can render the study results uninterpretable. The sponsor reserves the right to remove any study subject from the trial for non-compliance.

An individual subject is to be withdrawn from trial treatment if:

- The subject withdraws consent for trial treatment or trial participation, without the need to justify the decision.
- The subject can no longer be treated with trial medication for other medical reasons (such as surgery, adverse events, other diseases, or pregnancy)
- Development of a toxicity or adverse event which warrants risankizumab discontinuation including but not limited to SAEs or Suspected Unexpected Serious Adverse Reactions (SUSAR)s.
- If prohibited treatment is used during the study for any indication, the subject must discontinue use of the prohibited treatment if he/she wishes to continue in the study. In case of undue safety risk for the subject, the subject should discontinue study treatment at the discretion of the investigator. If the subject received a live virus vaccination during the study, the subject must discontinue study treatment
- If a subject experiences an intolerable increase of psoriasis during the course of the trial the subject will be discontinued from the trial to receive rescue treatment as deemed appropriate by the investigator
- The subject has repeatedly shown to be non-compliant with important trial procedures and, in the opinion of the investigator, is not willing or able to stick to the trial requirements in the future.

Discontinuation of study medication should not lead to withdrawal from the study. If possible the subject should complete all study visits and procedures as initially planned.

Given the subject's agreement, the subject will undergo the procedures for premature discontinuation and follow up as outlined in [Appendix C](#). If a subject becomes pregnant, refer to Section [6.1.6](#) for instructions on treatment termination.

For all subjects the reason for withdrawal (e.g., AE) must be recorded in the eCRF. These data will be included in the trial database and reported.

5.4.2 Discontinuation of Entire Study

AbbVie may terminate this study prematurely, either in its entirety or at any study site, for reasonable cause provided that written notice is submitted in advance of the intended termination. The investigator may also terminate the study at his/her site for reasonable cause, after providing written notice to AbbVie in advance of the intended termination. Advance notice is not required by either party if the study is stopped due to safety concerns. If AbbVie terminates the study for safety reasons, AbbVie will immediately notify the investigator by telephone and subsequently provide written instructions for study termination.

5.5 Treatments

5.5.1 Treatments Administered

Subjects in each group will receive either 150 mg or 75 mg of risankizumab at Week 0, 4 and every 12 weeks after. All products will be supplied by BI.

5.5.2 Identity of Investigational Products

Information about the risankizumab formulation to be used in this study is presented in [Table 3](#).

Table 3. Description of Test Product Risankizumab

Substance:	Risankizumab
Pharmaceutical form:	[REDACTED]
Source:	Boehringer Ingelheim Pharma GmbH & Co. KG
Chemical form:	Anti-human IL-23p19 mAb
Molecular weight	Approximately 148 kDa
Unit Strength:	75 mg risankizumab in a pre-filled syringe, concentration 90 mg/mL
Route of administration:	Subcutaneous injection
Posology:	Week 0, Week 4, then every 12 weeks
Duration of use:	172 weeks

5.5.2.1 Packaging and Labeling

The investigational products will be provided by BI. They will be packaged and labelled in accordance with the principles of Good Manufacturing Practice (GMP). Re-supply to the sites will be managed via an IRT system, which will also monitor expiry dates of supplies available at the sites.

For details of packaging and the description of the label, refer to the ISF.

5.5.2.2 Storage and Disposition of Study Drug

Drug supplies will be kept in their original packaging and in a secure limited access storage area according to the recommended storage conditions on the medication label. A temperature log must be maintained for documentation.

If the storage conditions are found to be outside the specified range, the sponsor must be contacted immediately.

Trial medication must be securely stored, e.g., in a locked refrigerator or at a pharmacy. The medication may only be dispensed to trial subjects by authorized personnel as documented in the trial staff list.

5.5.3 Method of Assigning Subjects to Treatment Groups

Within each substudy, subjects will be randomized to receive risankizumab 75 mg or risankizumab 150 mg in a ratio of 1:1.

After the eligibility criteria are confirmed, the investigator or designee will randomize the subject on Day 1 (Visit 2) through IRT call or website entry. At visits where study medication is to be administered, study sites will be required to complete the medication resupply module in the IRT.

5.5.4 Selection and Timing of Dose for Each Subject

An IRT will be used to allocate medication to subjects through medication numbers. At visits where study medication is to be administered, study sites will be required to complete the medication resupply module in the IRT. These visits are specified in [Appendix C](#).

At randomization as well as subsequent medication administration visits, IRT will assign medication numbers. At visits after Week 16, subjects in the 75 mg arm who do not achieve GPP or EP Clinical Response may be uptitrated to receive 150 mg; this process will be managed through IRT. Site personnel will enter the kit numbers in the eCRF.

Study drugs will be administered subcutaneously. Injections will be given with each subject receiving 1 or 2 injections of risankizumab at each dosing visit. Syringes will be administered per [Appendix C](#) schedule as assigned by IRT.

Risankizumab will be administered as a subcutaneous injection in the abdomen, thighs, gluteal regions, or upper arms (contra-lateral to that used for PK/ADA samples). Injections should be at least 2 cm apart and should not be close to a vein. The injection sites should avoid sites of psoriasis involvement as well as sites where the skin is tender, bruised, erythematous, or indurated, and should be alternated to other areas for subsequent doses.

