1.2 Synopsis

AbbVie Inc.	Protocol Number: M15-988
Name of Study Drug: ABBV-066	Phase of Development: 3
Name of Active Ingredient: Risankizumab	Date of Protocol Synopsis: 18 January 2017
Protocol Title: A Phase 3, Randomized, Open-Label Study to Assess Efficacy and Safety of Two Different Dose Regimens of Risankizumab Administered Subcutaneously in Japanese Subjects with Generalized Pustular Psoriasis or Erythrodermic Psoriasis	
Objective: The objective of this trial is to assess the long-term safety and efficacy of two different dose regimens of risankizumab in Japanese subjects with generalized pustular psoriasis (GPP) or erythrodermic psoriasis (EP).	
Investigator: Multicenter	
Study Sites: Multi-centre trial in Japan	
Study Population: Adult male or female subjects with a diagnosis of generalized pustular psoriasis or erythrodermic psoriasis.	
Number of Subjects to be Enrolled: Approximately 16 subjects will be randomized, 8 with generalized pustular psoriasis and 8 with erythrodermic psoriasis.	
Methodology: This is a 172 week randomized, open-label, parallel design study with two substudies, Substudy GPP and Substudy EP for subjects with generalized pustular psoriasis and subjects with erythrodermic psoriasis, respectively. In each Substudy, subjects will be randomized in 1:1 ratio to one of the two dose regimens of risankizumab. Subjects in each group will receive either 150 mg or 75 mg of risankizumab at Week 0, 4 and every 12 weeks after. From Week 16, subjects in the 75 mg group with no clinical response will be uptitrated to 150 mg. The primary efficacy evaluation will be performed at Week 16 and an assessment of long-term maintenance of response will be performed over 52 weeks.	
Diagnosis and Main Criteria for Inclusion/Exclusion:	
Main Inclusion:	
1. Male or female subjects, age \geq 20 years at screening. 2. Signed and dated written informed consent prior to admission to the study in accordance with Good Clinical Practice (GCP) and local legislation.	
For generalized pustular psoriasis	

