5.0 Investigational Plan

5.1 Overall Study Design and Plan: Description

This trial is a randomized, open-label study of two different dose regimens of risankizumab, 150 mg (2 syringes, 75 mg each) or 75 mg (1 syringe) at Week 0, 4 and every 12 weeks in two populations (subjects with GPP and with EP). Starting after the Week 16 visit, subjects on 75 mg may increase dosage to 150 mg. In total, at least 16 subjects, 8 with generalized pustular psoriasis and 8 with erythrodermic psoriasis will be randomized in this trial.

Subjects are included in the trial once they have signed the informed consent. Subjects suitable after screening will be eligible to participate.

Figure 1. Trial Design

Visit Schedule

All subjects are to adhere to the visit schedule as specified in the [Appendix C](#). Each visit date (with its window) is to be counted from Day 1. If any visit has to be rescheduled, subsequent visits should follow the original visit date schedule. Additional visits for the purpose of re-testing of laboratory parameters or AE monitoring may be included as deemed necessary by the investigator.

Details of Trial Procedures at Selected Visits

Study procedures to be performed at each visit are listed in [Appendix C](#) and the respective protocol sections. Refer to Section [5.3.1.1](#) for explanations of procedures. Additional details on procedures at selected visits are provided below.

Measurement of vital signs should precede blood sampling and be assessed pre-dose at all dosing visits.

Patient reported outcomes (PRO)s should be completed by the subject on his/her own in a quiet area/room before any other visit assessments or treatments, and, if possible, before any interaction with the investigator or other members of the study team. At Visit 2 these questionnaires should be obtained before having the subject randomized.

Screening and Run-In Period(s)

No trial procedures should be done until the subject has consented to taking part in the trial.

Once consented, the subject is considered to be enrolled in the trial and has started screening. The subject number should be recorded on the enrollment log and registered in the Interactive Response System (IRT) as a screened subject.

The Screening Period (Visit 1) is from Day –42 to Day –1. Visit 1 procedures may be extended to two physical visits, if needed. Re-screening will be permitted.

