4.2 Design Diagram

This trial is a randomized, open-label study of two different dose regimens of risankizumab, 150 mg (2 syringes, 75 mg each) or 75 mg (1 syringe) at Week 0, 4 and every 12 weeks in two populations (subjects with GPP and with EP). Starting after the Week 16 visit, subjects on 75 mg may increase dosage to 150 mg. In total, at least 16 subjects, 8 with generalized pustular psoriasis and 8 with erythrodermic psoriasis will be randomized in this trial. From Week 16, subjects will be uptitrated to 150 mg if they have not achieved a clinical response (for subjects with GPP:at least "Slightly Improved" in the overall improvement rating from baseline according to JDA total score; for subjects EP: at least "Minimally Improved" in Clinical Global Impression-Global Improvement).

Figure 1. Trial Design

All subjects are to adhere to the visit schedule as specified in the Protocol Appendix C. Each visit date (with its window) is to be counted from Day 1. If any visit has to be rescheduled, subsequent visits should follow the original visit date schedule. Additional visits for the purpose of re-testing of laboratory parameters or AE monitoring may be included as deemed necessary by the investigator.

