10.3 Secondary Efficacy Endpoints

The following additional efficacy variables will be summarized at all visits in the ITT population:

For GPP:

- Proportion of subjects achieving a GPP Clinical Response at Week 52
- Proportion of subjects achieving $\geq 90\%$ reduction from baseline Psoriasis Area Severity Index (PASI) score (PASI 90) at Week 16
- Proportion of subjects achieving PASI 90 at Week 52

For EP

- Proportion of subjects achieving an EP Clinical Response at Week 52
- Proportion of subjects achieving PASI 90 at Week 16
- Proportion of subjects achieving PASI 90 at Week 52

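### The plan makes uptitration of 75 mg non-responders mandatory from Week 16 in some sections and optional after Week 16 in others, and the SAP does not label the switched subjects

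*Protocol*

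**What the plan says.** The rule appears in several places in the current text.

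- **Protocol synopsis (1.2):** "From Week 16, subjects in the 75 mg group with no clinical response will be uptitrated to 150 mg". Section 3.2 is also mandatory and also starts from Week 16.
- **Protocol 5.1, body text:** "Starting after the Week 16 visit, subjects on 75 mg may increase dosage to 150 mg". Figure 1 belongs to this section. Appendix J records its current text, which is mandatory, starts from Week 16 and applies to subjects without a clinical response.
- **Protocol 5.5.4, the dosing section:** "subjects in the 75 mg arm who do not achieve GPP or EP Clinical Response may be uptitrated to receive 150 mg", and this is placed at visits later than Week 16. It adds that the IRT manages the process and that kit numbers are entered in the eCRF.
- **SAP 4.2:** one paragraph repeats the permissive sentence of Protocol 5.1 and then says "From Week 16, subjects will be uptitrated to 150 mg if they have not achieved a clinical response".

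The schedule in Protocol 5.5.1 is: "Subjects in each group will receive either 150 mg or 75 mg of risankizumab at Week 0, 4 and every 12 weeks after". The Week 52 secondary endpoints in SAP 10.3 include "Proportion of subjects achieving a GPP Clinical Response at Week 52" for GPP and "Proportion of subjects achieving an EP Clinical Response at Week 52" for EP, with PASI 90 at Week 52 in both substudies. SAP 10.1 summarises efficacy by two arms, 150 mg or 75 mg, within each disease.

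**The concern.** Two things differ between the sections: whether a 75 mg non-responder must switch or only can, and the first visit at which 150 mg may be given. Sites following different sections could treat subjects in the same state differently.

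The 75 mg arm is there to give dose-response information and to evaluate efficacy at a lower dose (Protocol 5.6.1 and 5.6.4). By Week 52 some subjects reported under 75 mg may have been on 150 mg for several doses, and the SAP has no display that shows it. Deviation reporting is also affected. SAP 7.4 tabulates wrong treatment or incorrect dose, and a non-responder kept on 75 mg would be a deviation under the synopsis but not under Section 5.5.4.

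**Working it through.** The documents give no figure of their own to reproduce here. The sample size is set by feasibility and no hypothesis is tested.

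**Step 1: compare the wording.**

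| Place | Obligation | Timing | Non-response trigger |
|---|---|---|---|
| Protocol synopsis | will | from Week 16 | stated |
| Protocol 3.2 | will | from Week 16 | stated |
| Protocol 5.1, body text | may | after the Week 16 visit | not in the sentence |
| Protocol 5.1, Figure 1 (text in Appendix J) | will | from Week 16 | stated |
| Protocol 5.5.4 | may | visits after Week 16 | stated |
| SAP 4.2, earlier sentence | may | after the Week 16 visit | not in the sentence |
| SAP 4.2, later sentence | will | from Week 16 | stated |

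The trigger is broadly consistent. The obligation and the timing are not.

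**Step 2: build the dosing grid.** Week 0, Week 4, then every 12 weeks gives Weeks 0, 4, 16, 28, 40, 52. Week 16 is a dosing visit. Taking the Week 52 assessment as made before that visit's dose, five doses precede it: Weeks 0, 4, 16, 28 and 40.

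**Step 3: count doses for a 75 mg subject who is a non-responder at Week 16.** With *m* doses of 150 mg among the five, cumulative dose = 75 × (5 − m) + 150 × m = 375 + 75m mg.

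| First 150 mg dose | m | Cumulative dose before Week 52 |
|---|---|---|
| Week 16 | 3 | 375 + 225 = 600 mg |
| Week 28 | 2 | 375 + 150 = 525 mg |
| Week 40 | 1 | 375 + 75 = 450 mg |
| Never (permission not used) | 0 | 375 mg |

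The 150 mg arm receives 5 × 150 = 750 mg over the same period.

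**Step 4: how often this could arise.** The documents give no expected Week 16 response rate, so a range is assumed. Eight subjects per substudy randomised 1:1 gives about 4 per arm; the documents say at least 8, so 4 is also an assumption. With independent subjects and true response rate p, the chance of at least one Week 16 non-responder among 4 is 1 − p⁴:

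- p = 50%: 1 − 0.0625 = 94%
- p = 70%: 1 − 0.2401 = 76%
- p = 90%: 1 − 0.6561 = 34%
- p = 95%: 1 − 0.8145 = 19%

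**Step 5: look for handling in the SAP.** Sections 5.0, 6.0 and 10.1 to 10.4 do not mention uptitrated subjects. They are not a separate group, not counted as failures and not cut off at the switch. The only treatment change with a response rule is prohibited psoriasis medication, in Section 6.0. Section 14.0, on changes from the protocol, is marked not applicable, so the SAP does not claim to settle the matter.

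**The case against.** Several points against the concern carry weight.

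- **Softer readings exist.** In Section 5.1, *may* can express possibility, and *after the Week 16 visit* can mean once that visit's assessment is done. That would fit a rule running from Week 16. This stands for Section 5.1, so the firm timing conflict rests on Section 5.5.4, which places the switch at visits after Week 16 and makes it permissive for subjects already identified as non-responders.
- **The trigger is not missing from Section 5.1.** A reader of the body sentence alone might infer that any 75 mg subject could move up regardless of response. Figure 1 states the condition, so the documents do not support that.
- **Doses received are not lost.** A reader might infer that the treatment behind the 75 mg Week 52 results cannot be determined. The IRT assigns medication and kit numbers go into the eCRF, so it can be.
- **Investigator discretion is not shown.** In an open-label trial a permissive rule leaves room for judgement, but no section says that the investigator chooses, and the IRT logic is not in these documents.
- **The labelling gap has another cause.** Even if every section agreed, switched subjects would still sit under 75 mg in the two-arm summaries. This is correct, and the fix treats it separately.
- **The stakes are limited.** The primary endpoint is at Week 16 and all results are descriptive.

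What remains is a contradiction between the synopsis and Section 3.2 on one side and the dosing section on the other, repeated inside one SAP paragraph.

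**Conclusion.** The point holds as an internal inconsistency in a treatment rule. The current text disagrees on whether uptitration is mandatory and on the first visit at which it applies. For a 75 mg subject who is a non-responder at Week 16, the planned exposure before Week 52 ranges from no doses of 150 mg to three, or 375 to 600 mg cumulative. This rests on the stated 12-weekly schedule and on the Week 52 assessment preceding that visit's dose.

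The Week 16 primary endpoint is unaffected. Week 52 is affected only if there are 75 mg non-responders. What is unclear is the intended regimen and the meaning of the Week 52 result for the 75 mg arm, not what each subject was given.

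A reader might also size the problem at 25 percentage points per subject (1/4). That figure assumes exactly 4 subjects in the arm and would apply to any issue in an arm that small. It does not measure the effect of this conflict, which would also require the dose change to alter a subject's response, and the documents give no basis for estimating that.

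**What to change.** **Wording.** The sponsor should reconcile the Protocol synopsis, Sections 3.2, 5.1 (body text and Figure 1) and 5.5.4, and SAP 4.2 to one rule. It should say whether uptitration is mandatory or optional and name the first applicable visit. The IRT should be aligned with it. Which rule applies is for the sponsor's clinical team.

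**Reporting.** As a separate change, needed even under a consistent rule, the SAP should label post-Week 16 results for that arm as *75 mg with possible uptitration*. Beside each such result it should give the number of subjects uptitrated and the visit of the first 150 mg dose.

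**Cost.** A text amendment to the two documents, a check of the IRT logic, and a small addition to the planned tables. No new data are needed, because the IRT and eCRF already hold the switch information. If the protocol wording can no longer be changed, the reporting step can still be made before database lock.
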